Appendix 6 Study Monitoring

1. Member(s) of the Sponsor or designee will meet with the Investigator prior to the initiation of the study in order to assess the adequacy of the Investigator's patient population, facilities, and equipment, and to familiarize the Investigator with the protocol.
2. A member of the Sponsor or designee will meet with the Investigator after several of the subjects have initiated the study in order to ensure that the subjects are being properly selected, that adequate supplies for the study have been provided, and that the assignment of medication is properly recorded. In addition, the Study Monitor will verify that the Investigator follows the approved protocol and all approved amendments, if any, by reviewing the Investigator's regulatory documents, source document, Informed Consent Forms, and Case Report Forms of study subjects.
3. A member of the Sponsor or designee will meet with the Investigator when all subjects have completed the Final Visit of the study, in order to collect the Case Report Forms, unused study medications, and unused supplies and materials.
4. Interim monitoring visits and telephone consultations will be done by the Study Monitor, as necessary, to ensure the proper progression and document of the study.

Appendix 7 Sample SAS Code

The following SAS code will be used for multiple imputations using the Monte-Carlo Markov Chain method, where a separate model will be fit for each time point at each visit.

```
proc mi data = indata seed = 6876 out = outdata1;  
  
mcmc initial = em;  
  
var trt01pn baseline IOP;  
  
run;
```

where

- *indata* is the name of the input dataset
- *outdata1* is the name of the output dataset
- *trt01pn* is the name of the treatment group variable in numeric format
- *baseline* captures the baseline IOP for the given time point
- *IOP* is the name of the IOP measure.

Thirty complete data sets will be generated from the above code. Each complete data set will be used to analyze this primary efficacy endpoint separately using analysis of variance. Then, the SAS procedure MIANALYZE will be used to analyze the results from the 30 complete data sets to generate a combined inference. The following SAS code will be used:

```
ods output diffs = outdata2;  
  
proc mixed data= outdata1;  
  
by _IMPUTATION_;  
  
class trt01pn;  
  
model IOP = trt01pn baseline;  
  
lsmeans trt01pn / cl pdiff;  
  
run;
```

```
proc sort data= outdata2;
```

```
    by trt01pn _trt01pn;
```

```
run;
```

```
ods output ParameterEstimates = outdata3;
```

```
proc mianalyze data= outdata2 alpha = 0.05;
```

```
    by trt01pn _trt01pn;
```

```
    class trt01pn _trt01pn;
```

```
    modeleffects estimate;
```

```
    stderr;
```

```
run;
```

where

- *outdata1* is the name of the input dataset from Proc MI
- *_IMPUTATION_* is the imputation number
- *trt01pn* is the name of the treatment group variable in numeric format
- *IOP* is the name of the IOP measure
- *baseline* captures the baseline IOP for the given time point
- *outdata2* is the name of the output dataset that contains the statistical results of the difference between treatment groups
- *outdata3* is the name of the output dataset that contains summary and inferential statistics.

1. PURPOSE OF THE ANALYSES

This statistical analysis plan (SAP) is being developed after review of the Aerie Pharmaceuticals, Inc., protocol number AR-13324-CS205 (dated 17 July 2017) but before any analyses of the data. The SAP contains detailed information to aid in the performance of the statistical analysis and reporting of the study data for use in the final clinical study report (CSR). This SAP is being written with due consideration of the recommendations outlined in the most recent International Conference on Harmonization (ICH) E9 Guideline entitled: Statistical Principles for Clinical Trials and the most recent ICH E3 Guideline, entitled: Structure and Content of Clinical Study Reports.

This SAP describes the data that will be analyzed and the subject characteristics, efficacy, and safety assessments that will be evaluated. This SAP provides details of the specific statistical methods that will be used. If additional analyses are required to supplement the planned analyses described in this SAP, they may be completed and will be identified in the CSR.

2. PROTOCOL SUMMARY

2.1 Study Objectives

The primary objectives of this study are to evaluate:

- The ocular hypotensive efficacy of netarsudil ophthalmic solution relative to its placebo over a 28-day period
- The ocular and systemic safety of netarsudil ophthalmic solution relative to its placebo over a 28-day period

The secondary objectives of this study are to evaluate:

None.

2.2 Overall Study Design and Plan

This is a 28-day, double-masked, randomized, multicenter, placebo-controlled, parallel-group efficacy and safety study evaluating elevated intraocular pressure (IOP) with netarsudil ophthalmic solution. The purpose of this study is to assess the efficacy and safety of netarsudil ophthalmic solution (0.02% and 0.04%) compared to its placebo in Japanese or Japanese-American subjects that are at least 18 years of age with open-angle glaucoma (OAG) or ocular hypertension (OHT).

All investigational products will be dosed in both eyes (OU) once daily (QD) in the evening (PM). Subjects eligible to be enrolled in this study will be those of Japanese ethnicity within the second generation, with a diagnosis of either OAG or OHT that are on treatment with a topical ocular hypotensive medication. A total of approximately 180 subjects will be enrolled in this study at approximately 35 clinical sites, all in United States, comprising a total of approximately 60 subjects per treatment arm for each of 3 treatment arms. Subjects who are enrolled in this study will be those at least 18 years of age with diagnosed OAG or OHT, each of whom meets all inclusion criteria and none of the exclusion criteria.

There will be a total of 6 visits designated as V1 – V6. For visits 3, 4, 5, and 6, the subjects will be evaluated at multiple time points (08:00, 10:00, and 16:00 hours) within the visit day. These time points will be designated as visit x.0, x.1, and x.2 respectively. The total treatment period is 28 days, starting at Visit 3 (Day 1), and there are follow-up visits at Week 1, Week 2, and Week 4.

At Screening (Visit 1), an examination will be conducted, including measurements of heart rate and blood pressure (vital signs), urine pregnancy test (for women of child bearing potential), and an ophthalmic examination to include ocular symptoms, best corrected visual acuity (BCVA), central corneal thickness by pachymetry (may be taken within 1 week of Visit 1), intraocular pressure (IOP; before pupil dilation. Medicated IOP must be ≥ 15 mmHg and < 30 mmHg in both eyes at the Screening Visit (this also applies to treatment naïve subjects), biomicroscopy, and dilated ophthalmoscopy). Visual fields and gonioscopy may be taken up to three months

prior to randomization (Visit 3). Subject symptoms will be queried and blood samples will be taken for clinical chemistry and hematology. All individuals who are qualified for enrollment will have their current ocular hypotensive therapy reviewed to determine the appropriate washout period, prior to Visit 2, as specified in Section 5.7.1 of the protocol.

At Visit 2 (Qualification #1, 08:00 hours), potential study subjects will be questioned with respect to changes in their health (to be recorded as medical history) and concomitant medication use. Study inclusion/exclusion criteria will be reassessed to confirm eligibility. Symptomatology, vital signs, BCVA, IOP, and biomicroscopy assessments will again be performed. The potential subject must have a post-washout IOP ≥ 15 mmHg (OAG) or ≥ 22 mmHg (OHT) and < 35 mmHg in both eyes to qualify for further participation. [REDACTED]

Qualified subjects will return for Visit 3 (Qualification #2, Baseline, Day 1) 2 to 7 days after Visit 2 at 3 time points. Inclusion/exclusion criteria will be reviewed again for the qualified individual at all the 3 time points. At Visit 3.0 (08:00 hours), the subject will be questioned regarding any changes in their health and concomitant medication use. The testing will include recording symptomatology, vital signs, BCVA, IOP, and biomicroscopy assessments. Any symptoms reported at this visit should be entered into medical history. The potential subject must have a post-washout IOP ≥ 15 mmHg (OAG) or ≥ 22 mmHg (OHT) and < 35 mmHg in both eyes to qualify for further participation. [REDACTED]

Qualifying subjects will return for two additional visits on this day (Visit 3.1 at 10:00 hours and Visit 3.2 at 16:00 hours) during which symptomatology, IOP, and biomicroscopy assessments will be performed. The potential subject must have a post-washout IOP ≥ 15 mmHg (OAG) or ≥ 22 mmHg (OHT) and < 35 mmHg in both eyes to qualify for further participation. [REDACTED]

In summary, the following IOP criteria must be met at the qualifying visits in both eyes for the subject to qualify for the study:

Visit, Day, Time	OAG Eyes IOP Requirement (mmHg)	OHT Eyes IOP Requirement (mmHg)
Visit 2, 8:00 hours	≥ 15 & < 35	≥ 22 & < 35
Visit 3.0, Day 1, 8:00 hours	≥ 15 & < 35	≥ 22 & < 35
Visit 3.1, Day 1, 10:00 hours	≥ 15 & < 35	≥ 22 & < 35
Visit 3.2, Day 1, 16:00 hours	≥ 15 & < 35	≥ 22 & < 35

For each qualification visit, individuals who do not meet the IOP requirement may return for up to 2 additional unscheduled qualification visits within 1 week of failing the specific qualification visit. Individuals returning at an unscheduled visit within 1 week are required to only re-measure IOP in both eyes. Upon return, such individuals would need to qualify at 08:00, 10:00 and 16:00

hours to continue the study. Individuals who fail due to IOP being ≥ 35 mmHg in either eye (exclusion criterion) MAY NOT return for additional qualification visits.

At this point, eligible subjects will be enrolled and assigned to an investigational product through an IWRS according to a computer-generated randomization list. The study medication kit containing 2 bottles will be dispensed through the IWRS to the eligible subject, along with dosing and storage instructions.

For each subject, both eyes will be treated. Subjects will be:

- Instructed to self-administer their masked medication at home between 20:00-22:00 hours (8 PM - 10 PM) beginning with the evening dose on that day

Subjects will return for post-treatment Visits 4.0, 4.1, and 4.2 (Week 1 [Day 8]; 08:00, 10:00, and 16:00 hours), Visits 5.0, 5.1, and 5.2 (Week 2 [Day 15]; 08:00, 10:00, and 16:00 hours), Visits 6.0, 6.1, and 6.2 (Week 4 [Day 29]; 08:00, 10:00, and 16:00 hours).

Symptomatology/adverse events (AE), review of concomitant medications and non-dilated eye examinations including IOP and biomicroscopy will be conducted at all of these visits. Vital signs and BCVA will also be conducted at Visits 4.0, 5.0 and 6.0. Any symptoms reported, or clinical signs observed which have worsened, either from baseline or from previous visits at these post-dose visits, will be recorded as treatment emergent adverse events (TEAE). At Visit 6 (Week 4 [Day 29]), a urine pregnancy test (for women of child-bearing potential) will be performed and blood will be drawn for clinical labs. A dilated ophthalmoscopy will be performed at Visit 6.2 (Week 4 [Day 29], 16:00 hours).

A study schedule of events table is presented in Appendix 1.

2.3 Study Population

The study population includes subjects aged 18 years of age or older with a diagnosis of OAG or OHT in both eyes (OAG in one eye and OHT in the fellow eye is acceptable). Subjects must be of Japanese ethnicity within the second generation proven by birth certificate or family tree. Japanese generation is defined as follows: 1st generation is defined as born in Japan, immigrated to US; 2nd generation is defined as parents are 1st generation, however, the subject was born in US as an American citizen. Subjects must have medicated intraocular pressure (IOP) ≥ 15 mmHg and < 30 mmHg in both eyes at screening visit (this also applies to treatment naïve subjects). For OAG eyes, unmedicated (post washout) IOP must be ≥ 15 mmHg and < 35 mmHg in both eyes at 2 qualification visits (08:00 hour), 2-7 days apart. At second qualification visit IOP ≥ 15 mmHg and < 35 mmHg at 10:00 and 16:00 hours (in both eyes). For OHT eyes, unmedicated (post washout) IOP must be ≥ 22 mmHg and < 35 mmHg in both eyes at 2 qualification visits (08:00 hour), 2-7 days apart. At second qualification visit IOP ≥ 22 mmHg and < 35 mmHg at 10:00 and 16:00 hours (in both eyes). The specific inclusion and exclusion criteria can be found in Sections 4.2 and 4.3 of the study protocol.

2.4 Treatment Regimens

There will be 3 treatments in this study:

- Netarsudil 0.02%, QD
- Netarsudil 0.04%, QD
- Placebo, QD

Subjects will be instructed to self-administer their masked medication QD in the evening between 20:00 – 22:00 hours (8pm - 10pm). All treatments will be dosed OU. The treatment period will be 28 days.

2.5 Treatment Group Assignments or Randomization

A randomization code for allocating the treatments was prepared by an independent biostatistician, who was not involved in the day-to-day conduct of the study, and provided in confidence to the unmasked clinical supply manager personnel at Aerie, the unmasked director of quality assurance at Aerie, and the Interactive Web Response (IWR) system personnel. At Visit 3.2 (Day 1), qualified subjects will be randomized in a 1:1:1 ratio to receive netarsudil 0.02%, netarsudil 0.04%, or placebo (stratified by investigative site). Treatment assignments were masked to the Investigator, the Sponsor team members involved in the day-to-day oversight of the clinical study and employees of the CRO administering the study for the Sponsor, and the study subjects. At the end of the study, the randomized treatment assignments will be presented in a data listing.

2.6 Sample Size Determination

Assuming a 2-sided test with $\alpha = 0.05$ and a common standard deviation (SD) of 3.5 mmHg at each time point yielding a common SD of 3.0 for the diurnal mean assuming a correlation among time points of 0.60, 49 ITT subjects per arm yields at least 90% power to demonstrate superiority of netarsudil (0.02% or 0.04%) to placebo in mean diurnal study eye IOP (average of 08:00, 10:00, and 16:00 hours) at the Week 4 visit assuming a difference of at least 2.0 mmHg in the mean diurnal IOP. The study will be considered a success and superiority of netarsudil to placebo will be concluded if the two-sided p-value ≤ 0.05 at Week 4. With 60 intent-to-treat (ITT) subjects per arm, each test has 95% power to demonstrate superiority of netarsudil (0.02% or 0.04%) to placebo.

3. GENERAL ANALYSIS AND REPORTING CONVENTIONS

This section discusses general policies to be employed in the analysis and reporting of the data from the study. Departures from these general policies may be given in the specific detailed sections of this SAP. When this situation occurs, the rules set forth in the specific section take precedence over the general policies.

All continuous study assessments will be summarized by treatment and time point (as applicable) using descriptive statistics (n, mean, median, standard deviation (SD), minimum, and maximum). All categorical study assessments will be summarized by treatment and time point (as applicable) using frequency counts and percentages.

All study data will be listed by treatment, subject, visit, and time point (as applicable). Hypothesis testing, unless otherwise indicated, will be performed at a 2-sided 0.05 significance level. When applicable, two-sided 95% confidence intervals will be reported. All p-values will be displayed to four decimal places, with p-values less than 0.0001 presented as '<0.0001' and p-values greater than 0.9999 presented as '>0.9999'. Differences between each netarsudil group and placebo will be calculated as netarsudil – placebo.

For diurnally adjusted IOP, baseline will refer to the time-relevant measure at Visits 3.0 through 3.2 (e.g. IOP at 08:00 hours at Visit 3.0 will be the baseline for 08:00 hours at Visits 4.0, 5.0, and 6.0, etc.; IOP at 10:00 hours at Visit 3.1 will be the baseline for 10:00 hours at Visits 4.1, 5.1, and 6.1, etc.). For mean diurnal IOP, baseline will refer to the mean diurnal IOP at Visit 3. For all other variables, baseline is defined as the last measurement prior to the first dose of study medication. Change from baseline will be calculated as follow-up visit – baseline visit.

The unit of analysis for efficacy will be the study eye, defined as the eye with the higher IOP at 08:00 hours on Visit 3. If both eyes have the same IOP at 08:00 hours on Visit 3, then the right eye will be the study eye.

All study data will be listed by subject, treatment, and time point (as applicable). In the listings, individual subjects will be identified by a combination of site number and subject number, e.g., XXX-YYY, where XXX is the site number and YYY is the subject number.

All data analysis will be performed by [REDACTED] after the study is completed and the database has been locked and released for un-masking. Statistical programming and analyses will be performed using SAS® Version 9.4 or higher. Output will be provided in rtf format for tables and pdf format for tables, listings, and figures.

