7.3 Treatment Period

7.3.1 Visit 3.0 (Qualification Visit #2, Day 1, for IOP and safety measurements at 08:00 hours)

Within 2 to 7 days after Visit 2, individuals will return to the Investigator’s office for the next 08:00 hour IOP measurement.

The results of the clinical laboratory tests from Visit 1 need to be available, and reviewed by the Investigator. In order for the individual to be enrolled, the tests CANNOT be indicative of any clinically significant disease in the opinion of the Investigator.

The subject will be questioned regarding any changes in their health or concomitant medication use. Any change in the individual’s health status should be recorded on the Medical History page of the CRF (e.g., the subject has been diagnosed with cancer).

Inclusion/exclusion criteria will be reviewed again for the qualified individual.

The following procedures will be performed:

- Heart rate and blood pressure
- Symptomatology: Individuals will be asked “How are you feeling?”

- Best Corrected Visual Acuity
- A non-dilated eye examination will be performed, including IOP measurements and biomicroscopy. IOP must be measured within 30 minutes of the nominal time (i.e., 07:30 to 08:30 hours)

For further evaluation of OAG eyes in the study, at this time, unmedicated (post washout) IOP must be ≥ 15 mmHg and < 35 mmHg in both eyes. For further evaluation of OHT eyes in the study, at this time, unmedicated (post washout) IOP must be ≥ 22 mmHg and < 35 mmHg in both eyes. [REDACTED]

Qualified individuals will continue with the measurements of IOP at 10:00 hours and 16:00 hours.

Individuals who do NOT meet the IOP requirements above may return for up to 2 additional qualification visits within 1 week of failing this qualification visit. Individuals returning at an unscheduled visit within 1 week are required to only re-measure IOP in both eyes.

Upon return for an unscheduled qualification visit, such individuals' IOP measurements would need to qualify at 08:00, 10:00, and 16:00 hours. Individuals who fail due to IOP being ≥ 35 mmHg in either eye (exclusion criterion) MAY NOT return for additional qualification visits.

Individuals are allowed to leave the Investigator's office between assessments, and eat and drink with no restrictions. However, individuals are not to consume alcohol or engage in strenuous exercise.

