7.3.2 Visit 3.1 (Day 1, for IOP and safety measurements at 10:00 hours)

Inclusion/exclusion criteria will be reviewed again for the qualified individual. Qualified individuals will be examined. Each examination will include:

- Symptomatology: Individuals will be asked "How are you feeling?"
- A non-dilated eye examination will be performed, including IOP measurements and biomicroscopy. IOP must be measured within 30 minutes of the nominal time (i.e., 09:30 to 10:30 hours)

For further evaluation of OAG eyes in the study, at this time, unmedicated (post washout) IOP must be ≥ 15 mmHg and < 35 mmHg in the same eye. For further evaluation of OHT eyes in the study, at this time, unmedicated (post washout) IOP must be ≥ 22 mmHg and < 35 mmHg in the same eye. [REDACTED]

Qualified individuals will continue with the qualification visit. Individuals who do NOT meet this requirement may return for up to 2 additional qualification visits within 1 week of failing this qualification visit. Individuals returning at an unscheduled visit within 1 week are required to only re-measure IOP in both eyes.

Upon return for an unscheduled qualification visit, such individuals would need to qualify at 08:00, 10:00 and 16:00 hours. Individuals who fail due to IOP being ≥ 35 mmHg in either eye (exclusion criterion) MAY NOT return for additional qualification visits.

Individuals are allowed to leave the Investigator's office between assessments, and eat and drink with no restrictions. However, individuals are not to consume alcohol or engage in strenuous exercise.

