9. PLANNED STATISTICAL METHODS

9.1 General Considerations

All continuous study assessments will be summarized by treatment and time point (as applicable) using descriptive statistics (n, mean, median, standard deviation, minimum, and maximum). All categorical study assessments will be summarized by treatment and time point (as applicable) using frequency counts and percentages.

Hypothesis testing, unless otherwise indicated, will be performed at a 2-sided 0.05 significance level. When applicable, two-sided 95% confidence intervals will be reported. All p-values will be displayed to four decimal places, with p-values less than 0.0001 presented as '<0.0001' and p-values greater than 0.9999 presented as '>0.9999'. Differences between netarsudil (0.02% or 0.04%) and placebo will be calculated as netarsudil – placebo.

All study data will be listed by treatment, subject, and time point (as applicable).

For diurnally-adjusted IOP, baseline will refer to the time-relevant measure at Visit 3.0 through 3.2 (e.g., IOP at 08:00 hours at Visit 3.0 will be the baseline for 08:00 hours at Visit 4.0, Visit 5.0, and Visit 6.0; IOP at 10:00 hours at Visit 3.1 will be the baseline for 10:00 hours at Visit 4.1, Visit 5.1, and Visit 6.1; etc.). For all other variables, baseline is defined as the last measurement prior to the first dose of study medication. An additional definition of baseline for conjunctival hyperemia will also be used: baseline (pre-washout) will be defined as the conjunctival hyperemia measure at Visit 1.

The unit of analysis for efficacy will be the study eye. For a subject who qualifies, the study eye will be the eye with the higher IOP at 08:00 hours on Visit 3. If both eyes have the same IOP at 08:00 hours on Visit 3, then the right eye will be the study eye.

Data collected during the observation extension visits may be summarized separately from the data collected during the main portion of the study.

Statistical methods will be more fully described in separate document(s) (i.e., the Statistical Analysis Plan).

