- ⁴ Ocular symptoms: Subjects will be queried at each visit “How are you feeling?” and treatment emergent AEs beginning at Visit 4 will be documented on the AE form. Additional symptoms reported after screening and before randomization will be documented on the medical history form. Adverse events will be recorded for every study visit (i.e., at 08:00, 10:00, and 16:00 hours) as needed.
- ⁵ Individuals returning at an Unscheduled Visit within 1 week to re-attempt IOP qualification are required to only re-measure IOP in both eyes.
- ⁶ Gonioscopy evaluation up to 3 months prior to randomization is acceptable.
- ⁷ Ultrasound pachymetry within 1 week prior to screening is acceptable.
- ⁸ Entry visual field evaluation up to 3 months prior to randomization is acceptable. Visual field collection must meet the requirement for automated threshold visual field assessment (e.g., 30-2 or 24-2 Humphrey) and reliability.
- ⁹ Collect kit(s) dispensed during the Day 1 visit.

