8.1.2 Assessment Time Windows

In general, it is intended that all safety and efficacy data (with some exceptions) will be summarized at each time point collected regardless of assessment time windows. Because subjects may have an early termination visit at any time or may have unscheduled visits, the following conventions will be implemented.

For all safety data, the visit date or start date (e.g., adverse events) will be used to calculate study day, defined as the number of days from the day of first dose. The day of first dose (Visit 3) is considered study day 1, so study day will be computed as (date of data – Visit 3 + 1). Study day will be presented in listings for medical history, concomitant medications, and adverse events.

In all by-visit safety assessments, end of study visits and early termination visits will be combined in order to present all data available for each subject; early termination visits will not be windowed into the nearest fitting study visit. Each subject will have one end of study visit.

For efficacy outcomes, early termination data will not be combined with end of study visit information as the timing of the outcome measure is integral to the analysis. Instead, the efficacy outcome will be windowed into the nearest study visit, where Week 1 visit has a ± 2 day window and Week 2 and Week 4 visits have a ± 3 day window.

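### Does the plan leave baseline IOP, study eye and Day 1 undefined for subjects who fail Visit 3 on low IOP and qualify at a later unscheduled visit?

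*SAP*

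**What the plan says.** Both documents attach the IOP baseline to Visit 3. Protocol 9.1 states: "For diurnally-adjusted IOP, baseline will refer to the time-relevant measure at Visit 3.0 through 3.2". SAP section 3 repeats this for the time-matched values and adds, for the primary endpoint, "For mean diurnal IOP, baseline will refer to the mean diurnal IOP at Visit 3". The study eye is the eye with the higher 08:00 reading at that visit. Variables other than IOP take the latest value before dosing, a rule that leaves IOP out.

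Dates hang on the same label. SAP 8.1.2 says "The day of first dose (Visit 3) is considered study day 1". SAP 5.1 and 9.2 note that the first-dose date is not collected and take the Visit 3 date in its place.

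Requalification is allowed. Under SAP 2.2, subjects who miss the IOP requirement "may return for up to 2 additional unscheduled qualification visits within 1 week of failing the specific qualification visit", and they must then qualify at 08:00, 10:00 and 16:00. Footnote 5 of Protocol Appendix 1 reads "Individuals returning at an Unscheduled Visit within 1 week to re-attempt IOP qualification are required to only re-measure IOP in both eyes".

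**The concern.** A requalified subject can have two or three candidate sets of readings, and neither document says in words which set is Visit 3. SAP 8.1.2 seems about to settle it ("Because subjects may have an early termination visit at any time or may have unscheduled visits, the following conventions will be implemented"), but the conventions that follow cover study day and early termination only.

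The failed visit may also be incomplete. After the 08:00 reading, "Qualified individuals will continue with the measurements of IOP at 10:00 hours and 16:00 hours" (Protocol 7.3.1), and after the 10:00 reading, "Qualified individuals will continue with the qualification visit" (Protocol 7.3.2). A subject who failed at either hour has no full diurnal set under the original label. A subject who failed at 16:00 has a full set, but from a day on which the subject was not eligible.

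Baseline mean diurnal IOP is the covariate in the primary model and the reference for the diurnal change endpoints, and SAP 8.1.1 rules out imputation. A programmer who filtered strictly on the label could lose a subject, or use the wrong baseline, study eye or start date, while another programmer would not.

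**Working it through.** **The plan's own figures.** Inputs from SAP 2.6: SD 3.5 mmHg per time point, correlation 0.60, difference 2.0 mmHg, two-sided alpha 0.05. The SD of the diurnal mean is 3.5 × √((1 + 2 × 0.60)/3) = 2.997, which rounds to the stated 3.0. Noncentral-t power is 0.904 at 49 per arm and 0.952 at 60, matching the stated 90% and 95%. At the roughly 10 per arm now expected (SAP 8.2) it is 0.29. None of this depends on how Visit 3 is defined.

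**Can a failed visit be Visit 3?** What the plan requires of that visit:

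| Place | What Visit 3 must be | Can a failed visit be this? |
|---|---|---|
| SAP 2.2, IOP table | Thresholds met at 3.0, 3.1 and 3.2 | No |
| SAP 2.5; Protocol 7.3.3 | Randomization at 3.2, on Day 1 | No |
| Protocol 7.3.3 | Kit dispensed at 3.2 | No |
| Protocol 3.3; SAP 2.2 | Start of treatment | No |
| SAP 8.1.2 | Day of first dose, study day 1 | No |
| SAP 8.3 | Diurnal baseline averages the three Day 1 readings | No, since Day 1 is the first-dose day |

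Every row fits the visit at which the subject qualified and was randomized. That visit must include all three hours, so a complete baseline set exists.

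Two further details agree. In the schedules of both documents, footnote 5 sits on the IOP cells of Visits 2, 3.0, 3.1 and 3.2, so the repeat readings are shown as part of those qualification visits. For the study eye, Protocol 7.3.3 places the rule just before randomization, and SAP 6.3 refers to a CRF page for study eye selection, so the site records the eye.

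**What the literal reading would cost.** Let the return come k = 1 to 7 days after the failed visit.

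- Exposure is last dose − Visit 3 + 1. Dated from the failed visit, a true 28 days becomes 28 + k = 29 to 35 days, an excess of k/28 = 3.6% to 25%.
- Precision, ignoring covariate adjustment: SE = 3.0 × √(1/n₁ + 1/n₂). With 10 and 10 it is 1.342, and with 9 and 10 it is 1.378 (+2.7%). With 8 and 10 it is 1.423 (+6.1%).
- Wrong baseline in one of 10 subjects in an arm. Assumed, because the documents give no values: the two visits differ by 1 to 5 mmHg and the covariate slope is 0.5 to 1.0. The adjusted difference moves by slope × difference / 10, from 0.5 × 1/10 = 0.05 to 1.0 × 5/10 = 0.50 mmHg. The upper end is 0.50/1.342 = 0.37 of a standard error.
- Visit windows: SAP 8.1.2 generally summarizes data at the time point collected, whatever the window, and windows efficacy data only from early termination visits. Its study-day formula is written for safety data. Scheduled efficacy visits of a requalified subject are unaffected.

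Each nonzero figure requires treating as Visit 3 a day that the table above rules out.

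**The case for a change.** The strongest reply is that an inference is not an operational rule. The first-dose date is set to the Visit 3 date, while Visit 3 is identified as the day of first dose. For a requalified subject that is circular, and nothing says that records stored under an unscheduled label should be moved to Visit 3. The rule that would settle the matter for IOP is written for other variables only. One sentence would close the gap at almost no cost, and at 10 per arm each subject counts.

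Part of this stands. The mapping sentence is absent, and the inference has to be drawn from several sections. The circularity is broken by randomization, which SAP 2.5 places at Visit 3.2 on Day 1 and which runs through the web response system. SAP 5.1 lists randomization information for each subject. A randomized subject with no baseline, or with a study start before randomization, would show up in routine data checks. How the database labels the repeat readings cannot be seen from these documents. If they are stored under Visit 3, the question never arises.

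**Conclusion.** No change is needed. The plan implies, without stating it, that the qualifying visit serves as Visit 3 for a requalified subject, and it is hard to follow its other provisions on any other reading. An analyst would take baseline IOP, study eye and Day 1 from the 08:00, 10:00 and 16:00 set at which the subject qualified and was randomized. A written rule would only record that choice.

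The stakes are small in any case. The issue touches only requalified subjects, of whom there may be none. It arises before randomization, so it does not by itself bias the comparison between arms. No sample size, power or alpha figure moves. SAP 8.2, 8.3.1 and section 13 present the efficacy results for information, without statistical inference.

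This rests on two assumptions: that the qualifying readings and the randomization date are available to the analysts, and that the analysts read the label together with its stated function.
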